2.2 BRIEF DESCRIPTION OF STUDY DESIGN

Standard Care Arm: Airway management in the standard care arm of this pragmatic trial will be dictated by local protocols. We will accrue data on all participants who met all the inclusion criteria and none of the exclusion criteria regardless of which airway management strategy is utilized.

Initial SGA Arm: EMS agencies randomized to the intervention arm will follow a strategy of initial advanced airway management with an SGA. Airway management of eligible subjects will be initiated at any time between EMS initial contact and the transfer of care to the receiving trauma center. Only the initial advanced prehospital airway management strategy is dictated by the study protocol; all other interventions, including preparation and subsequent attempts at advanced airway management, will be dictated by local protocols.

In the event that a prehospital provider is unable to complete preparations, such as bag valve mask ventilation, and place an advanced airway, the subject will be retained and analyzed according to the intended arm assignment.

In both arms, study data will be abstracted from EMS records, including indications for airway management, vital signs, use of adjuncts, pharmacological treatment, and timing of interventions and will be entered into an electronic data management system.

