2.4.4 Rescue Strategy

Only the initial attempt at advanced airway management is dictated by study protocol. All subsequent attempts at management will be at the provider's discretion and will be based on local protocol.

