2.5 STUDY ENDPOINTS

Primary Outcome: The primary outcome for the trial is 24-hour survival.

Secondary Outcomes: Secondary outcomes include survival to hospital discharge, expected clinical events (including incorrect placement of the airway, inadequate ventilation, airway trauma, or concern for aspiration as defined as documented vomiting and/or need for suctioning), airway management performance (including initial pass success, overall success, and use of rescue technique), ICU length of stay, ventilator days, and expected adverse events including airway trauma, pneumothorax, incidence of acute respiratory distress syndrome (ARDS) and incidence of ventilator associated pneumonia (VAP).

Primary Outcome Definition:

24-hour Mortality: A binary variable defined as death within 24 hours

Secondary Outcome Definitions:

Secondary outcomes will be assessed from arrival at the trauma center through day 30 or discharge, whichever is first.

In-Hospital Mortality: A binary variable defined as death recorded any time after hospital arrival.

Airway Management Performance: The elements of airway management performance include airway misplacement (including endotracheal tube misplacement), initial pass success (the successful placement of device on the first attempt past the teeth confirmed by EtCO₂), sequence of airway insertion, airway insertion success and time, number of airway insertion attempts, inadequate ventilation, and any instances of airway conversion (change of airway in the first 24 hours).

Acute Respiratory Distress Syndrome (ARDS): The Berlin definition for mild ARDS ($\text{PaO}_2/\text{FIO}_2 \leq 300$ mm Hg plus timing, imaging, and origin criteria) will be utilized as a threshold value to determine the incidence of ARDS within 24 hours of presentation. We will further stratify patients into mild, moderate ($\text{PaO}_2/\text{FIO}_2 \leq 200$ mm Hg), or severe ($\text{PaO}_2/\text{FIO}_2 \leq 100$ mm Hg) ARDS.¹⁶

ICU length of stay (LOS): Defined as the number of days spent admitted to the Intensive Care Unit. ICU LOS will be recorded to the first decimal place.

Ventilator Days: Defined as number of days on a mechanical ventilator. Ventilator days will be recorded to the first decimal place.

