Hypothesis #1: For the primary outcome, an indicator of death within 24 hours will be generated for each participant. A generalized linear mixed model (i.e. logistic regression model) will be used to assess the independent impact of initial SGAs on 24-hour survival, with a random effect of randomization unit a fixed effect for each step, and fixed effects of airway management (standard vs. initial SGA) and the potential confounding effects of baseline characteristics. The estimated intra-randomization unit correlation and time effect from this model will be reported to help design future randomized trials and to describe the potential confounding effects of calendar time. For time-to-event data, a mixed effects Cox-proportional hazards regression model will be used to assess the independent impact of airway management strategy on time to death, with randomization unit as a random effect and step, airway management strategy, and the potential confounding effects of baseline characteristics not balanced through random assignment as fixed effects.

Hypothesis #2: The same analytic approach that was carried out for hypothesis #1 will be implemented, but the outcome of interest will be survival to hospital discharge.

Hypothesis #3: The analytic approach for the secondary outcomes will vary based on the type of outcomes. For binary outcomes (e.g., 24-hour and in hospital mortality, ventilator associated pneumonia, and post-traumatic ARDS), the same analytic approach that was carried out for Hypothesis #1 will be implemented. For continuous outcomes (e.g., hypotension or hypoxia dose) a generalized linear mixed model (i.e., linear model) will be used to assess the independent effect of airway management strategy on outcome, with a random effect of randomization unit, a fixed effect for each step, and fixed effects of airway management strategy (standard airway versus initial SGA) and the potential confounding effects of baseline characteristics.

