2.6.6 Interim Analyses

Prior to initiation, and in concert with the DSMB, the final monitoring plan will be developed to serve as a guide to the DSMB's decision-making process concerning early stopping of the trial. In making the decision to recommend termination of the trial, the DSMB will be guided by information on safety outcomes by treatment group.

Two interim safety analyses will be conducted, one at the completion of the second step (third period) and one at the completion of the fourth step (fifth period, out of seven periods). The frequency of the composite safety outcome (mortality, failure to place an advanced airway on first attempt, failure to

ventilate) in the two groups will be summarized. The null hypothesis that there is no difference in the proportion of the rate of the composite safety outcome between the two groups will be tested using a generalized linear mixed model. Group sequential methods, such as a Lan and Demets approach with an O'Brien and Fleming spending function will be used to ensure that the overall type I error rate of 0.05 is maintained across the three tests (two interim and one final), with the majority of the type I error reserved for the final test. Based on the expected recruitment of 287 participants per period (2,009/7 periods), we expect a sample size of 861 for the first interim analysis (information fraction of 43%) and 1,435 for the second interim analysis (information fraction of 71%). For the first interim analysis the upper/lower boundaries will be ± 3.22 with a nominal alpha level of 0.001. The second interim analysis will have upper/lower boundaries of ± 2.42 with a nominal alpha level of 0.015. The final analysis will have upper/lower boundaries of ± 2.00 with a nominal alpha level of 0.045.

Further—and in relation to the interim safety analyses—safety data by group will be provided periodically to the DSMB. Safety data serious adverse events include frequency, a description of each event, and the date of each event.

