2.6.9 Data Elements

Prehospital Elements: To include (but not be limited to) scene time, vital signs, times and description of prehospital interventions, procedure type(s), device type(s), airway adjuncts used, rapid sequence intubation, associated medications and dosages used, number of procedure attempts, reason for failed attempt(s), progression to surgical airway, time to successful airway management, time to advanced airway, procedure complications, time and dose of any medications administered (for induction, post intubation sedation, and resuscitation), transport time, vital signs during transport, times and description of interventions provided during transport, and mode(s) of transport (e.g. ground, air). Also includes provider level data—including level of training—and system level data, including staffing, service volume, frequency of airway management, and ambulance location (rural/urban).

In-Hospital Elements: To include (but not be limited to) relevant vital signs, relevant laboratory studies (including arterial blood gases), and interventions (especially time to extubation and/or reintubation as applicable). Ventilator associated pneumonia, post-traumatic acute respiratory distress syndrome (ARDS), and patient disposition will also be collected.

Outcome Elements: To include (but not be limited to) 24-hour survival, hospital length of stay, length of stay in ICU, ventilator days, and in-hospital survival through day 30.

Exploratory Analyses: To include (but not be limited to) associations that may represent the underlying mechanisms associated with airway management's effect on 24-hour survival. When the necessary data are available, we will examine time to definitive airway, exposure to hypoxia,

superoxia, hypotension, hypocarbia and hypercarbia. Exposure will be examined as a categorical value and as a continuous variable calculated as a function of depth (calculated from a given normal value) times duration. The value of this expression will be regressed to look for an association with mortality.

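### Airway insertion time falls by default under a linear model that can only use placed airways; if final success differs by arm and failures tend to be slow cases, the arm with more failures can look faster than it is

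*Combined protocol and SAP*

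**What the plan says.** Section 2.5 defines airway management performance through several elements, among them "airway insertion success and time, number of airway insertion attempts". It gives no start, no stop and no value for a patient in whom no airway was placed. Section 2.6.9 collects "time to successful airway management, time to advanced airway"; as worded, both need a placed airway. The same section adds, as an exploratory item that depends on available data, that "we will examine time to definitive airway".

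On method, Section 2.6.1 (Hypothesis #3) states: "For continuous outcomes (e.g., hypotension or hypoxia dose) a generalized linear mixed model (i.e., linear model) will be used". The only time-to-event model stands under Hypothesis #1 and concerns the "independent impact of airway management strategy on time to death". The Hypothesis #3 paragraph has no time-to-event branch.

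On failures, Section 2.2 says that when the crew cannot complete preparations and "place an advanced airway, the subject will be retained and analyzed according to the intended arm assignment". Section 2.4.4 adds: "Only the initial attempt at advanced airway management is dictated by study protocol". Section 2.6.6 includes "failure to place an advanced airway on first attempt" in the composite safety outcome. Section 2.6.7 names multiple imputation for 24-hour mortality only.

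**The concern.** A linear model for insertion time can use only patients who have one. Whether an airway was placed is decided after assignment, and the trial compares strategies that may differ in exactly that. Keeping a failed patient in the assigned arm, as Section 2.2 does, does not help this outcome, because there is no number to analyse. The comparison becomes one among successes, and the arm that fails more often is the more strongly selected.

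Speed is part of the case for the supraglottic airway. Section 1.2 links delayed airway management to worse outcome, and Section 1.3 cites speed and ease of insertion. Sections 1.2 and 2.4.2 describe intubation as error-prone and supraglottic devices as easier to place. If that expectation holds for final success as well, a successes-only mean would tend to understate a speed advantage of the initial supraglottic strategy.

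**Working it through.** **Plan's own figure.** There is none for insertion time. The sample size in Section 2.6.2 concerns 24-hour mortality and is not an input here.

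**Route through the plan.**
1. Insertion time is continuous and belongs to a secondary outcome (Section 2.5).
2. The stated method for continuous outcomes is a linear mixed model (Section 2.6.1).
3. A patient with no airway before transfer of care has no time (Sections 2.2 and 2.6.9).
4. Section 2.6.7 does not fill the gap. Its named imputation is for mortality, and its general idea of predicting missing outcomes from observed individuals would here predict failures from successes, which carries the same selection.

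**Assumed inputs.** Log time is normal with standard deviation s, identical in both arms, so the true difference is zero. A proportion p ends with a placed airway. Failures are the patients highest on a latent score that has correlation r with log time; r = 1 means that the slowest patients are exactly the failures.

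**Formula.** The mean time among successes, relative to the mean in all patients, is Φ(z_p − r·s)/p. The ratio of two such terms is the apparent effect.

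**80% against 90%, r = 1** (z = 0.8416 and 1.2816):
- s = 0.4: (0.6706/0.8)/(0.8110/0.9) = 0.8383/0.9011 = 0.930, or 7% shorter
- s = 0.6: (0.5955/0.8)/(0.7522/0.9) = 0.7443/0.8358 = 0.891, or 11% shorter
- s = 0.8: (0.5166/0.8)/(0.6849/0.9) = 0.6457/0.7610 = 0.849, or 15% shorter

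**Apparent shortening in the lower-success arm, same formula:**

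| Final success | r | s = 0.4 | s = 0.6 | s = 0.8 |
|---|---|---|---|---|
| 80% vs 90% | 1 | 7.0% | 10.9% | 15.1% |
| 80% vs 90% | 0.5 | 3.3% | 5.1% | 7.0% |
| 80% vs 90% | 0.3 | 1.9% | 3.0% | 4.0% |
| 95% vs 97% | 1 | 2.0% | 3.3% | 4.9% |
| 95% vs 97% | 0.5 | 0.9% | 1.4% | 2.0% |
| equal success, or r = 0 | – | 0 | 0 | 0 |

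**In minutes.** Assume a median of 5 minutes and s = 0.6, so the mean is 5 × exp(0.18) = 5.99. With 5% against 15% failures, the arm with more failures looks 0.66 minutes faster at r = 1, 0.52 at 0.8, 0.32 at 0.5, 0.19 at 0.3 and 0 at r = 0.

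**Can the sign reverse?** Let one arm be truly 10% slower (+0.60 minutes), with failures of 10% against 2% and r = 1. Its mean among successes is 1.1 × 5.99 × 0.8358 = 5.50 minutes. The other arm's is 5.99 × Φ(2.0537 − 0.6)/0.98 = 5.99 × 0.9459 = 5.66. The slower arm looks 0.16 minutes faster.

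**Check of the remedy.** With identical true times and the slowest patients failing, keeping failures and ranking them longest gives a median of 5.0 minutes in both arms. The false difference disappears.

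**The case against.** The strongest reply is that the plan is silent rather than wrong. No section assigns insertion time to the linear model by name; the examples given are hypotension and hypoxia dose. No section says that failures are discarded, and Section 2.6.7 assumes that data are not missing at random and promises sensitivity analyses. The first part stands: a reader might infer that the plan prescribes dropping failures, and the documents do not say so. The omission follows by default, because the only rule for continuous outcomes is linear and a never-placed airway has no time. The general missing-data text ties no method to this outcome.

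A second reply is that rescue limits the loss. Attempts after the first are open under Section 2.4.4, and Section 3.1 requires agencies capable of both techniques. A failed first device can therefore still lead to a time, unless time means the first device only, which is undefined. This stands, and it makes large gaps in final success uncertain.

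Third, the largest percentages require the slowest patients to be exactly the failures. Early abandonment or a short transport would weaken that link. This stands too, so the r = 1 rows are a ceiling.

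Finally, insertion time has little weight in the plan, and success rates are themselves secondary outcomes, so a failure difference would be visible beside the times. Visibility helps the reader but does not correct the estimated time difference.

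**Conclusion.** The point holds in conditional form. Following the plan as written leads to a comparison of insertion time among successes only. That comparison favours the arm with more failures if final success differs between arms and failures tend to be slow cases. Both conditions are needed.

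The size cannot be computed from the documents. Under assumed success of 80% against 90% it is at most 7% to 15% of the mean, and about 3% to 7% at a failure-time correlation of 0.5. For 95% against 97% it is at most 2% to 5%. It is zero if success is equal or unrelated to time.

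A reader might go further and infer that one named arm will look falsely fast, or that a bias of 10% or more is to be expected. The documents support neither: they give no success rate for either arm, and rescue attempts may narrow any gap. The matter concerns one element of a secondary outcome. The 24-hour survival analysis and the sample size are unaffected.

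**What to change.** In the SAP:

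1. Define the start and stop of the time from timestamps already collected under Section 2.6.9. State whether it runs to the first device or to any successful advanced airway, and which start applies to patients enrolled from a referral hospital.
2. Analyse it in all enrolled patients as time to event: cumulative incidence of a successful airway by arm, with the same step and randomization-unit terms as the other models.
3. Count patients with no airway placed as not achieved by transfer of care, so that they stay in the denominator. Treat death before placement as a competing event.
4. Report the result beside the success rates, and keep the mean among successes as description only.

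The cost is SAP wording. If the times are taken from those already listed, no new data are needed, and neither the sample size nor clinical care changes. The downside is a summary slightly less simple than a difference in means.

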Ventilator Associated Pneumonia: A binary variable defined as VAP in the first 24 hours as evident by a new infiltrate on chest image and ≥ 1 of the following: temp >38 or less than 36 degrees C, WBCs $>12,000$, purulent secretions from the airways and or reduction in gas exchange ($\text{PaO}_2/\text{FIO}_2 \leq 300$ mm Hg). (Michetti Trauma 2012)

Other Adverse Events: Binary variables defined as the onset of one of the following adverse events in the first 24 hours after enrollment: oropharyngeal trauma, hypopharyngeal trauma, pneumothorax, aspiration pneumonitis, ARDS, and VAP.

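### VAP and ARDS carry both a day-30 and a 24-hour window; under the 24-hour one, later onsets are not counted and day-1 lung injury can count as VAP

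*Combined protocol and SAP*

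**What the plan says.** Section 2.5 introduces its secondary outcome definitions with one window: "Secondary outcomes will be assessed from arrival at the trauma center through day 30 or discharge, whichever is first". The definitions that follow do not keep to it.

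- **ARDS:** the mild Berlin threshold (PaO2/FIO2 at or below 300, "plus timing, imaging, and origin criteria") "will be utilized as a threshold value to determine the incidence of ARDS within 24 hours of presentation".
- **VAP:** "A binary variable defined as VAP in the first 24 hours as evident by a new infiltrate on chest image", together with at least one of four items: abnormal temperature, a white cell count above 12,000, "purulent secretions from the airways and or reduction in gas exchange". The gas-exchange item is again PaO2/FIO2 at or below 300. No time zero and no minimum time on a ventilator are given.
- **Other adverse events:** "Binary variables defined as the onset of one of the following adverse events in the first 24 hours after enrollment". The list that follows includes ARDS and VAP, and also aspiration pneumonitis, for which no criteria are given.

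Section 2.6.1 names VAP and post-traumatic ARDS as binary outcomes under Hypothesis #3, to be analyzed with the mixed model used for the primary outcome. Section 2.6.9 lists both among the in-hospital data elements with no 24-hour limit. Section 3.3 states that the interventions are finished before the patient reaches the hospital.

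**The concern.** Two features of these definitions bear on the VAP and ARDS comparisons.

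First, the same outcome has two windows of very different length and up to three starting points. Sites could abstract to different rules, and the analyst would have to choose between them after the data exist. If the 24-hour rule is applied, a case with later onset is recorded as no event.

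Second, the VAP rule shares its oxygenation threshold with ARDS, and both need imaging. Day-1 lung injury with a new infiltrate can therefore be recorded as pneumonia.

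Fewer counted events lower power. Events that are not pneumonia, if equally common in both arms, pull the observed risk ratio towards 1. Both make a null result on lung complications look more reassuring than it is.

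A smaller matter is that the general window opens at arrival. First-pass success, misplacement and inadequate ventilation in the field happen before that.

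**Working it through.** **1. Windows, tested on cases.**

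- *Ventilated patient with pneumonia starting after day 1.* Counted under the general sentence; not counted under the VAP definition or the adverse-event list.
- *ARDS starting more than 24 hours after enrollment but within 24 hours of presentation.* Counted under the ARDS definition; not counted under the adverse-event list. This assumes that presentation means hospital arrival, which the plan does not say. Section 3.3 places enrollment at the enrolling agency's time on scene.
- *New infiltrate and PaO2/FIO2 at or below 300 on day 1.* These two findings alone satisfy VAP. If the Berlin timing, imaging and origin criteria also hold, the patient is an ARDS case too. No rule assigns patients who meet both.

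The overlap is partial. VAP can be met through temperature, white cells or secretions with no oxygenation criterion, and ARDS has requirements that VAP lacks.

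**2. The plan's own sample size, to validate the formula used next.** The plan states no rate, sample size or power for VAP or ARDS. Section 2.6.2 gives 16.7% versus 9.7%, 80% power, 5% significance (two-sided assumed), ICC 0.025, 17 agencies, 7 periods and N = 1,904, which is 1,904/(17 × 7) = 16 per agency-period. Individual randomization needs 366 per arm, 732 in total. The cross-sectional stepped-wedge factor is 2.573 at 16 per agency-period, so N = 1,883; at 17 it is 2.591, so N = 1,897. Both are close to 1,904.

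As a cross-check on power, SE² = v·p̄(1 − p̄), with

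v = I·s²(s² + Tτ²) / [(IU − W)s² + (U² + ITU − TW − IV)τ²].

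Here I = 17, T = 7, τ² = 0.025 and s² = 0.975/16 = 0.0609. Agencies are assumed to step 3, 3, 3, 3, 3, 2, which gives U = 62, V = 272, W = 784. The bracketed terms are 270 and 1,110, so v = 0.2444/44.20 = 0.00553. For the primary outcome p̄ = 0.132, SE = 0.0252, and power = Φ(0.07/0.0252 − 1.96) = 0.79, near the stated 80%.

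**3. Late onsets (illustration only).** Assumed: day-30 control incidence 10% or 20%, risk ratio 0.7, the primary outcome's ICC, N = 1,904. Let f be the share of day-30 cases that start within 24 hours. Example at 10% and f = 0.5: rates 0.05 and 0.035, p̄ = 0.0425, SE = 0.0150, power = Φ(1.00 − 1.96) = 0.17.

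| f | Events, power at 10% | Events, power at 20% |
|---|---|---|
| 1 | 162, 0.30 | 324, 0.58 |
| 0.5 | 81, 0.17 | 162, 0.30 |
| 0.25 | 40, 0.10 | 81, 0.17 |
| 0.1 | 16, 0.06 | 32, 0.09 |

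**4. Events that are not pneumonia (illustration only).** Assumed: 15% day-30 incidence, f = 0.25, true risk ratio 0.7. The true 24-hour rates are 0.0375 and 0.02625. If a further 2% of each arm meets the definition without having VAP, the observed ratio is 0.04625/0.0575 = 0.80. At 5% it is 0.07625/0.0875 = 0.87, and at 10% it is 0.12625/0.1375 = 0.92.

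**5. Death before onset.** On the plan's mortality figures, 83.3% (standard) and 90.3% (SGA) survive day 1. Since 90.3/83.3 = 1.08, about 8% more SGA patients would remain at risk of a later event. A longer window therefore has to deal with death.

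**The case against.** The strongest defense is that the 24-hour limit is deliberate. It appears three times for these outcomes, airway conversion is also limited to 24 hours, the primary outcome is at 24 hours, and section 2.6.7 describes a short, mostly prehospital intervention. A specific definition normally overrides a general sentence, and that sentence cannot literally fit first-pass success. ARDS by Berlin criteria within 24 hours is also an interpretable early outcome.

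This stands as a plausible account of intent. It does not settle the matter. The override is not stated, the starting points still differ or are missing, and as a deliberate choice it still drops every later onset and still lets day-1 lung injury qualify as VAP.

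Two further objections are fair. Even with every day-30 case counted, the 10% illustration gives power of only 0.30, so a longer window does not make this a well-powered comparison. And the arrival start matters little in practice, because attempts, failures and complications are abstracted from EMS records in both arms.

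A reader might infer that most VAP and ARDS cases will be missed. The documents do not support that: they give neither incidence nor onset timing, and the word needs f below 0.5. Nor do they show that VAP becomes a near-duplicate of ARDS, since how often the two coincide is not given.

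**Conclusion.** The conflict between windows and the overlap of criteria are both certain from the text. Under the 24-hour definitions, VAP and ARDS with onset after 24 hours are not counted, and a day-1 patient with a new infiltrate and PaO2/FIO2 at or below 300 can be counted as VAP and, if the other Berlin criteria are met, also as ARDS.

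The size of either effect cannot be derived from the documents. The power and risk-ratio figures rest on the assumed incidences, onset shares, effect and false-positive rates, and show direction and range only.

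It would be tempting to conclude that Aim 3 as a whole fails. That goes too far. Aim 3 concerns major adverse events generally, and nothing shows that a 24-hour window loses cases of airway trauma or pneumothorax. The effect is confined to the VAP and ARDS comparisons under Hypothesis #3; the primary outcome and its sample size are untouched. The point should be corrected, but it does not threaten the trial's main conclusion.

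**What to change.** - Analyze VAP and ARDS over the plan's own window, through day 30 or discharge, from one stated time zero, and align sections 2.5 and 2.6.9.
- Record the onset date of each, so that onset within 24 hours can still be reported as an early-event analysis.
- State how a patient who meets both definitions is classified.
- Account for death before onset as a competing event, for example by reporting cumulative incidence beside a cause-specific hazard comparison. The mixed-effects Cox model already in section 2.6.1 can supply the latter.
- Start the window for airway-performance and other prehospital events at enrollment.

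The cost is revised wording, an onset-date field, and somewhat more chart abstraction of imaging and blood gases after day 1. ICU stay, ventilator days and in-hospital survival through day 30 are already collected, but no section promises review of imaging or gases to that point. Some later data will be lost to withdrawal, because the EFIC plan stops collection once a subject withdraws.
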